#### 1.3.1.4 Prior studies with other HDAC inhibitors in breast cancer

A second phase II (ENCORE 301) trial evaluated entinostat and exemestane and treated patients with advanced estrogen receptor (ER)-positive breast cancer. This study recently received Breakthrough Therapy designation from the FDA for its potential to reverse resistance to hormonal therapies. The median PFS was 4.3 months versus 2.3 months, for entinostat and placebo, respectively (HR = 0.73; P = 0.06). The median overall survival in the combination arm was 28.1 m compared to 19.8 m in the exemestane arm (HR = 0.59; P = 0.036). The objective response rate to the combination was 6.3%, while to exemestane alone was 4.6% (P = 0.58).

### 1.4 Rationale for the Dose Selection/Regimen

The rationale and justification for pembrolizumab, vorinostat, and tamoxifen dosing, route of administration, planned maximum dosage, and regimen are as defined in the previously conducted pilot study (NCT02395627).

### 1.5 Correlative Studies

Immune checkpoint inhibitors have revolutionized cancer therapy, yet have limited efficacy in estrogen receptor (ER+) breast cancer. Implicated factors include scarcity of tumor-infiltrating lymphocytes (TILs), low PD-L1 expression, female gender, and liver involvement. In vitro and in vivo studies suggest that epigenetic modulation with HDAC inhibitors modulate regulatory T cells (Treg) and change TIL composition, which is further associated with the presence of a specific immune signature.

Patients with ER+ metastatic breast cancer, who progressed on multiple prior therapies, were treated with tamoxifen in combination with vorinostat and pembrolizumab either immediately or after 3 weeks of epigenetic priming in a phase II trial. Comprehensive flow-cytometric immunophenotyping, PD-L1 staining, and histone acetylation were evaluated on tumor and blood cells.

34 patients (median age 56 years (32-81), heavily pretreated with a median of 5 (2-13) prior regimens received at least one dose of vorinostat and evaluable for response. Grade  $\frac{3}{4}$  toxicities in 2 pts each (6%) included immune hepatitis, fatigue, and thrombocytopenia. Grade 2 toxicities were pneumonitis and colitis in 3%, fatigue in 27% and thrombocytopenia in 12% pts. Six patients did not receive pembrolizumab due to rapid progression or toxicity. Clinical benefits rate defined as CR, PR, and stable disease  $> 6$ m was seen in 5/28 (18%) of patients. Tumor lymphocyte infiltration and PD-L1 expression were low. High expression of PD-1/CTLA-4 dual staining in CD8 cells of  $>20\%$  in tumor or blood was seen in 5 patients overall, 4/5 (80%) patients with benefit and in one other patient, who was withdrawn due to immune hepatitis in week 3. Both tumor and peripheral blood CD8 PD-1/CTLA-4 dual expression strongly correlated with time to progression and reduction in Foxp3+/CTLA-4high Treg population in tumors by vorinostat.

Our data highlight the potential for patient selection based on exhausted CD8+ cells in blood or tumor to predict response to immune checkpoint inhibitors in a small subset of ER+ breast cancer patients (NCT02395627).

## 2 Study Objectives

### 2.1 Hypothesis

Given the above data, we hypothesize that HDAC induced epigenetic priming in a biomarker enriched study will increase the efficacy of pembrolizumab with patient selection based on exhausted CD8+ cells in blood or tumor in a small subset of (ER)+ breast cancer patients.

Biomarker threshold for exhausted CD8+ will be set at 10% to avoid under-enrollment of patients with potential response.

Response further correlated with exhausted CD4 cells in blood (but not not tumors), thus we will allow enrollment of patients who have dual expression of PD-1 and CTLA4 on CD4 cells in blood only: biomarker threshold will be set at 5%.

Based on the below described earlier study results, we hypothesize that the pembrolizumab and TAM arm even in the setting of biomarker selection will not pass the first stage and will be stopped early after 11 patients and not expanded to 30 patients, whereas the immune priming by vorinostat arm will proceed to the second stage enrolling a total of 35. Under this hypothesis, we will most likely enroll 46 evaluable patients (~65% chance), whereas the possible enrollment ranges from 24 to 65. For the comparison of the treatment arms, the proposed design will have 72.53% power for the Z-test for two proportions conditioning on the study design, when the true response rates are 0.4 and 0.1 for the immune priming and the no immune priming treatment arm.

### 2.2 Primary Objective and Endpoints

Primary Objective	Endpoint(s)	Time Frame
To define the role of epigenetic immune priming in a biomarker enriched ER+ breast cancer population on the basis of overall response rate	ORR: CR+PR+SD	From time of initial response to time of progression or death, whichever occurs first, assessed up to 24 weeks

### 2.3 Secondary Objective(s) and Endpoint(s)

Secondary Objective	Endpoint(s)	Time Frame
1. To assess duration of response (DOR) 24-week landmark progression-free survival (PFS:24)	DOR (CR+PR)	From initiation of study treatment to time of progression or death, whichever occurs first, assessed up to 24 weeks
2. Median PFS and overall survival (OS)	
 
• Median PFS
 
• overall survival (OS)
 
	From initiation of study treatment to the time of death from any cause on study, assessed up to 48 months
3. Tumor responses will also be calculated by Immune Related Response-Criteria (irRC)	Tumor responses (irRC)	Through study completion, assessed up to 24 months

## 2.4 Exploratory (Correlative) Objectives

Exploratory Objective	Endpoint(s)
1. Evaluation of biomarker target threshold on response rate (retrospective cut off of 20% vs 10%)	Biomarker target threshold on response rate
2. To assess the ratio of effector T cells: regulatory T cells in blood and tumor biopsies pre- and post-therapy.	Ratio of effector T cells: regulatory T cells in blood and tumor biopsies pre- and post-therapy
3. To evaluate inflammatory T cell signature changes in blood and tumor biopsies pre- and post-therapy.	inflammatory T cell signature changes in blood and tumor biopsies pre- and post-therapy
4. To evaluate changes in number of myeloid-derived suppressor cells (MDSCs) in peripheral blood and tumor biopsies pre- and post-therapy.	changes in number of myeloid-derived suppressor cells (MDSCs) in peripheral blood and tumor biopsies pre- and post-therapy
5. To evaluate changes in histone acetylation in peripheral blood cells and tumor biopsies pre- and post-therapy	changes in histone acetylation in peripheral blood cells and tumor biopsies pre- and post-therapy
6. Initial comparison to vorinostat-induced PD-1 in lymphocytes, PD-L1 modulation	Comparison to vorinostat-induced PD-1 in lymphocytes, PD-L1 modulation
7. Nanostring and 10x sequencing and single cell immune phenotyping (on stored tissue for successful arms only)	Completion of Nanostring and 10x sequencing and single cell immune phenotyping (on stored tissue for successful arms only)
8. Impact of HDAC inhibition of response to pembrolizumab vs. pembrolizumab in biomarker enriched population	Impact of HDAC inhibition

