### 3.2 Sample Size

We adopt a randomized two-arm trial with futility early stopping built-in within each treatment arm using a Simon's two-stage design (Simon, 1989). The effect of vorinostat on pembrolizumab and the effect of pembrolizumab and tamoxifen in this biomarker-selected population of ER+ breast cancer patients will be first tested against the respectively chosen null rate in the first stage within the treatment arms and then compared between the treatment arms.

65 patients to be treated under the study/enrolled in the investigational portion of the study (sample size for primary objective).

**For Arm A (vorinostat + TAM + pembro):** The null hypothesis that the true response rate for pembrolizumab and vorinostat in ER+ pretreated patients alone without biomarker enrichment is 0.15 which will be tested against the alternative that response rate of pembrolizumab in a biomarker select population is 0.40. In the first stage, 13 patients will be accrued. If there are 2 or fewer responses in these 13 patients, the study will be stopped. Otherwise, 22 additional patients will be accrued for a total of 35. The null hypothesis will be rejected if 10 or more responses are observed in 35 patients. This design yields a type I error rate of 0.025 and power of 0.9 in this treatment arm when the true response rate is 0.4 in this patient subpopulation.

**For Arm B (pembro + TAM):** The null hypothesis that the true response rate for pembrolizumab in ER+ pretreated patients alone is 0.10 which will be tested against the alternative that response rate of pembrolizumab in a biomarker select population is 0.35. In the first stage, 11 patients will be accrued. If there are 1 or fewer responses in these 11 patients, the study will be stopped. Otherwise, 19 additional patients will be accrued for a total of 30. The null hypothesis will be rejected if 7 or more responses are observed in 30 patients. This design yields a type I error rate of 0.025 and power of 0.9 in this treatment arm when the true response rate of pembro + TAM treatment is 0.35 in this patient subpopulation.

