## 8 Statistical Considerations and Evaluation of Results

This is a randomized two-arm trial with futility early stopping built-in within each treatment arm using a Simon's two-stage design (Simon, 1989). The effect of vorinostat on pembrolizumab and the effect of pembrolizumab and tamoxifen in this biomarker-selected population of ER+ breast cancer patients will be first tested against the respectively chosen null rate in the first stage within the treatment arms and then compared between the treatment arms.

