### 8.1 Sample Size Considerations

#### 8.1.1 Sample Size and Power Estimate

For Arm A (pembro + vorinostat + TAM): The null hypothesis that the true response rate for pembrolizumab and vorinostat in ER+ pretreated patients alone without biomarker enrichment is 0.15 which will be tested against the alternative that response rate of pembrolizumab in a biomarker select population is 0.40. In the first stage, 13 patients will be accrued. If there are 2 or fewer responses in these 13 patients, the study will be stopped. Otherwise, 22 additional patients will be accrued for a total of 35. The null hypothesis will be rejected if 10 or more responses are observed in 35 patients. This design yields a type I error rate of 0.025 and power of 0.9 in this treatment arm when the true response rate is 0.4 in this patient subpopulation.

For Arm B (pembro + TAM): The null hypothesis that the true response rate for pembrolizumab in ER+ pretreated patients alone is 0.10 which will be tested against the alternative that response rate of pembrolizumab in a biomarker select population is 0.35. In the first stage, 11 patients will be accrued. If there are 1 or fewer responses in these 11 patients, the study will be stopped. Otherwise, 19 additional patients will be accrued for a total of 30. The null hypothesis will be rejected if 7 or more responses are observed in 30 patients. This design yields a type I error rate of 0.025 and power of 0.9 in this treatment arm when the true response rate of pembro and TAM treatment is 0.35 in this patient subpopulation.

Based on earlier results in Section 1.3 and hypothesized treatment effects, we will most likely to enroll 46 evaluable patients (~65% chance), whereas the possible enrollment ranges from 24 to 65. For the comparison of the treatment arms, the proposed design will have 72.53% power for the Fisher's exact test at 0.1 significance level when the true response rates are 0.4 and 0.1 for the immune priming and the no immune priming treatment arm.

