### 8.3.2 Primary Analysis (or Analysis of Primary Endpoints)

#### Primary Endpoint 1 Analysis (Evaluation of Efficacy)

For each arm objective response rate (ORR) will be defined as the proportion of participants randomized to that arm whose status is SD or better (CR, PR) at 24 weeks' follow-up. Within each treatment arm, the observed ORR will be compared to the respective null (ineffective) rate using the decision rule provided by the Simon's two-stage design. In addition to calculating the ORR, we will calculate the corresponding one-sided 95% confidence interval by appropriately accounting for the Simon's two-stage design: given the observed response number ( $s$ ), testing of the null hypothesis of  $H_0: p \leq p_0$  will reject the null if the probability of observing as many or less than the observed number of responses ( $s$ ) is less than the significance level:  $\text{Prob}(S \leq s | p_0) < \alpha$ . Using this hypothesis inversely, we can construct a  $(1-\alpha)100\%$  one-sided confidence interval is given as a set

$$\{p: \text{Prob}(S \leq s | p_0 = p) < \alpha\}$$

where  $\text{Prob}(S \leq s \mid p_0 = p)$  indicates the joint distribution of stage to stop and observed response number ( $s$ ) as in Chang et al., 1989. Similarly, the observed rates will be compared between the treatment arms using the Z-test and appropriately accounting for the Simon's two-stage design.

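### The A-versus-B comparison, the only analysis that isolates vorinostat, is exploratory in one place and primary in another, while Arm A's test against 15% is labelled a test of vorinostat

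*Combined protocol and SAP*

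**What the plan says.** Section 2.2 gives the primary objective: "To define the role of epigenetic immune priming in a biomarker enriched ER+ breast cancer population on the basis of overall response rate". The endpoint counts CR, PR and SD; section 8.3.2 fixes it at 24 weeks.

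The contrast between the arms appears in several places with different standing:

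- **Abstract, exploratory objective (h), and section 2.4, objective 8:** exploratory, worded as "Impact of HDAC inhibition of response to pembrolizumab vs. pembrolizumab in biomarker enriched population".
- **Section 8.3.2, Primary Analysis:** "Similarly, the observed rates will be compared between the treatment arms using the Z-test", with allowance for the two-stage design. No level or sidedness is given.
- **Section 2.1:** 72.53% power for a Z-test at true rates 0.4 and 0.1, no level given.
- **Section 8.1.1:** the same 72.53%, now for Fisher's exact test at level 0.1.

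Sections 3.2 and 8 describe what is tested within the arms, before the arms are compared: "The effect of vorinostat on pembrolizumab and the effect of pembrolizumab and tamoxifen in this biomarker-selected population of ER+ breast cancer patients". For Arm A, section 8.1.1 reads: "The null hypothesis that the true response rate for pembrolizumab and vorinostat in ER+ pretreated patients alone without biomarker enrichment is 0.15". The alternative is 0.40 in a biomarker-selected population. Arm B has null 0.10 and alternative 0.35.

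**The concern.** Every patient in Arm A receives vorinostat. The 0.15 null is the rate for pembrolizumab plus vorinostat in unselected patients, and the 0.40 alternative is the rate in selected patients. What changes between null and alternative is biomarker selection. Rejecting 0.15 is therefore evidence about the regimen in a selected population and says nothing specific about vorinostat.

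Section 1.3.1.2 recognises this confounding in the pilot, where all patients had vorinostat and the contribution of the biomarker could not be separated from that of the HDAC inhibitor. Arm B exists to separate them. Describing Arm A's own test as one of vorinostat's effect brings the confounding back.

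The stake is the trial's main inference. With no deciding rule, an analyst who has seen the data could rest the priming conclusion on the single-arm result (stated power 0.9, type I error 0.025) or on the randomized one (stated power 72.53%). Only the second answers the question.

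**Working it through.** **Inputs** (sections 3.2 and 8.1.1). Arm A: 13 patients in stage 1, stop at 2 or fewer responses; 35 in total, reject 0.15 at 10 or more. Arm B: 11 in stage 1, stop at 1 or fewer; 30 in total, reject 0.10 at 7 or more.

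**Formulas.** With b the binomial probability,

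- Arm A: P(reject; p) = Σ over x = 3 to 13 of b(x; 13, p) × P(Bin(22, p) ≥ 10 − x)
- Arm B: P(reject; p) = Σ over x = 2 to 11 of b(x; 11, p) × P(Bin(19, p) ≥ 7 − x)

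For A versus B, the test is applied to every pair of final outcomes, including arms stopped at stage 1, and the probabilities of the significant pairs are summed.

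**Step 1: reproduce the plan's figures.**

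| Quantity | Stated | Exact |
|---|---|---|
| Arm A type I error / power | 0.025 / 0.9 | 0.0249 / 0.9036 |
| Arm B type I error / power | 0.025 / 0.9 | 0.0220 / 0.9004 |
| A continues and B stops (0.4, 0.1) | about 65% | (1 − 0.0579) × 0.6974 = 65.7% |
| A versus B, two-sided Fisher, 0.10 (0.4, 0.1) | 72.53% | 72.44% |

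The between-arm power agrees with a two-sided Fisher test at 0.10. Other versions do not: one-sided Fisher at 0.10 gives 79.7%, and a pooled Z-test gives 78.8% (one-sided 0.05), 64.4% (two-sided 0.05) or 91.8% (one-sided 0.10).

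**Step 2: suppose vorinostat adds nothing.** Both arms then share one true rate p in selected patients.

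| Common rate p | Arm A rejects 0.15 | Arm B rejects 0.10 | Fisher (two-sided 0.1) favours A |
|---|---|---|---|
| 0.15 | 2.5% | 13.2% | 1.2% |
| 0.20 | 12.7% | 34.9% | 2.7% |
| 0.25 | 33.2% | 59.3% | 3.9% |
| 0.30 | 57.9% | 78.5% | 4.7% |
| 0.35 (Arm B's alternative) | 78.1% | 90.0% | 5.2% |

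Arm A's rejection probability passes 50% at p = 0.284.

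**Step 3: how often the two results part.** At p = 0.35, Arm A passes its own test and also shows a significant advantage over B in 5.1% of trials. Arm A therefore passes without such an advantage in 78.1% − 5.1% = 73.0%.

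**Step 4: bring in Arm B.** Given p, the arms are independent. Arm A passes and Arm B fails with probability 0.781 × (1 − 0.900) = 7.8% at 0.35, 0.579 × (1 − 0.785) = 12.5% at 0.30 and 0.332 × (1 − 0.593) = 13.5% at 0.25. At 0.35, trials with Arm A positive, Arm B negative and no significant difference make up 4.3%.

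**The case against.** A reader might infer that the randomized comparison has been demoted to exploratory, and that a useless vorinostat would usually be declared effective. The documents support neither.

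**Status.** Section 8.3.2 places the comparison in the primary analysis, sections 2.1 and 8.1.1 give it power, and sections 3.2 and 8 set the order: within-arm tests, then the comparison. The defect is contradictory status with no deciding rule.

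**Declaration.** No section says that rejecting Arm A's null shows vorinostat works. Section 1.3.1 separates the two aims, added effect of vorinostat and effect of biomarker selection.

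**Frequency.** The high figures need a selected, no-vorinostat rate above about 0.28. The sponsor expects Arm B to stop at stage 1 and uses 0.10 for it in the power statement; at a common rate of 0.10, Arm A rejects in 0.15% of trials. At 0.35 most of the 73.0% are trials in which Arm B also succeeds, and two positive arms with no significant difference do not invite a vorinostat claim.

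All of this stands and limits the size of the point. It does not remove the mislabelled test, the conflict over status or the missing rule. Nor is 0.35 an invented scenario: it is the rate Arm B is sized to detect.

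**Conclusion.** The point holds as a conflict in the plan that should be fixed. A versus B is the only analysis that isolates vorinostat; it is exploratory in the Abstract and section 2.4 and primary in section 8.3.2. Sections 3.2 and 8 attach vorinostat's effect to a test in which vorinostat does not vary. Nothing says which result settles the primary objective.

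The size depends on the selected rate without vorinostat, which the documents leave open between 0.10 and 0.35. With no vorinostat effect, Arm A passes its test in 78.1% of trials at 0.35, 33.2% at 0.25 and 2.5% at 0.15. These are probabilities of passing a single-arm screen. They become false claims about vorinostat only if Arm A's result is read without Arm B. The between-arm figures assume a two-sided Fisher test at 0.10, the version that reproduces the stated power.

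**What to change.** 1. In sections 2.2 and 8.3.2, state that any conclusion about epigenetic priming requires the A-versus-B comparison, and say whether Arm A must also pass its own screen. Either rule is defensible and controls the error similarly: at a common rate of 0.35, 5.2% for the comparison alone and 5.1% for both together.
2. Remove exploratory objective 8 in section 2.4 and item (h) in the Abstract.
3. In sections 3.2 and 8, replace the reference to vorinostat's effect on pembrolizumab with *the benefit rate of the triplet in biomarker-selected patients*, and add that Arm A's test alone supports no claim about vorinostat. Keep the Simon boundaries as arm-level screens.
4. Name one between-arm test, level and sidedness throughout. Sections 2.1 and 8.3.2 say Z-test; section 8.1.1 says Fisher at 0.1. Two-sided Fisher at 0.10 fits the stated power.

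The cost is protocol wording, with no change to sample size, patients or treatment. The downside is candour about power: the figure attached to the priming question becomes about 72.5% at two-sided 0.1, for rates 0.4 versus 0.1, in place of 90% at 0.025. If Arm B reached 0.35 and Arm A 0.40, the comparison would favour A in only 10.6% of trials.

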## 3 Study Design

### 3.1 Characteristics

We propose a single site Phase II, two-arm, open-label unblinded, 65-patient trial in patients with hormone therapy-resistant breast cancer (HTR) to test the role of epigenetic priming in a biomarker enriched patient population in HTR breast cancer. The two arms include Arm A: pembrolizumab, vorinostat, and tamoxifen and Arm B pembrolizumab and tamoxifen.

Patients will be evaluated for response at 9 weeks ( $\pm 1$  week) by RECIST1.1 (using IR-RECIST) and will continue on therapy if they have stable disease or response at the time of disease evaluations. Patients with progression on imaging but are clinically stable, may stay on study but will require follow-up staging after 4-6 weeks. Patients will be assessed continually for safety and tolerability as well as for any adverse events. If progression on therapy with pembrolizumab, patient may continue if clinically indicated and be re-evaluated after 4-8 weeks.

We will follow AEs of clinical interest as defined by Merck and will dose modify pembrolizumab as per Merck guidelines. We have significant prior experience with vorinostat, tamoxifen, and pembrolizumab combination and are facile with managing drug toxicities.

Tissue biopsies of all patients will be collected prior to enrollment to assess for pre-treatment of our immune signature and PD-L-1 expression. Follow up biopsies and peripheral blood collection will be taken from all patients post-treatment at 8-10 weeks to characterize changes in local tissue effects and antigen-specific cellular and humoral immune responses in peripheral blood.

Patients will be stratified by prior number of hormonal and chemotherapies.

### 3.2 Sample Size

We adopt a randomized two-arm trial with futility early stopping built-in within each treatment arm using a Simon's two-stage design (Simon, 1989). The effect of vorinostat on pembrolizumab and the effect of pembrolizumab and tamoxifen in this biomarker-selected population of ER+ breast cancer patients will be first tested against the respectively chosen null rate in the first stage within the treatment arms and then compared between the treatment arms.

65 patients to be treated under the study/enrolled in the investigational portion of the study (sample size for primary objective).

**For Arm A (vorinostat + TAM + pembro):** The null hypothesis that the true response rate for pembrolizumab and vorinostat in ER+ pretreated patients alone without biomarker enrichment is 0.15 which will be tested against the alternative that response rate of pembrolizumab in a biomarker select population is 0.40. In the first stage, 13 patients will be accrued. If there are 2 or fewer responses in these 13 patients, the study will be stopped. Otherwise, 22 additional patients will be accrued for a total of 35. The null hypothesis will be rejected if 10 or more responses are observed in 35 patients. This design yields a type I error rate of 0.025 and power of 0.9 in this treatment arm when the true response rate is 0.4 in this patient subpopulation.

**For Arm B (pembro + TAM):** The null hypothesis that the true response rate for pembrolizumab in ER+ pretreated patients alone is 0.10 which will be tested against the alternative that response rate of pembrolizumab in a biomarker select population is 0.35. In the first stage, 11 patients will be accrued. If there are 1 or fewer responses in these 11 patients, the study will be stopped. Otherwise, 19 additional patients will be accrued for a total of 30. The null hypothesis will be rejected if 7 or more responses are observed in 30 patients. This design yields a type I error rate of 0.025 and power of 0.9 in this treatment arm when the true response rate of pembro + TAM treatment is 0.35 in this patient subpopulation.

